#### **Hypothesis**

 $\begin{aligned} &H_0: \, \mu_c = 0 \\ &H_A: \, \mu_c \neq 0 \end{aligned}$ 

Where  $\mu_c$  is the mean change from baseline to the 3-Month Visit in worst-pain score.

#### **Data Collection**

At the baseline and 3-Month study visits, the worst pain question in the BPI will be used to evaluate the pain severity:

Please rate your pain by circling the one number that best describes your pain at its worst in the last 24 hours (circle only one number, 0-10). No pain = 0, Pain as bad as you can imagine = 10

#### **Endpoint Definition**

Change in pain will be calculated as:

[figure not shown]
μc = worst-pain 3-month – worst-pain baseline

A negative value for change in pain represents a lowering of the subject's pain score (an improvement, or reduction in pain) and a positive value represents an increase in the subject's pain score (a worsening, or increase in pain).

#### **Analysis Methods**

Revision 1.0

Page 11 of 15

The main analysis for the primary objective hypothesis testing will be on the Primary Objective Cohort using the Completers Analysis Set.

A two-sided t-test with alpha=0.05 will be used to test the null hypothesis of no change in worst-pain score between baseline and 3 months. If the p-value is <0.05, the primary objective will be demonstrated, and statistical significance will be declared.

If the distribution of the change scores does not meet the assumption of normality, by calculating the Shapiro-Wilk W statistic probability, the non-parametric Wilcoxon signed-rank test will be used to test for significant change with alpha=0.05, two-sided. P-values less than 0.05 for the Shapiro-Wilk statistic will indicate non-normality.

In order to include all the treated subjects in the analysis, a sensitivity analysis will be performed on the Treated Analysis Set. The endpoint data will first undergo multiple imputations (MI). Rather than filling in a single value for each missing value, MI replaces each missing value with a set of "plausible" values that represent the uncertainty about the correct value to impute. These multiple imputed datasets are then analyzed using standard statistical procedures and then combined into one analysis result with an appropriately increased variance. The model variables in the MI analysis may include the following when deemed appropriate: the endpoint variable at 3 months and the endpoint variable at baseline, 3 days, 1 week, and 1 month, baseline covariates of subject age, Karnofsky score, and time from primary cancer diagnosis to baseline. The method to be used is the Markov chain Monte Carlo (MCMC) method of SAS (version 9.4 or higher). This is an iterative method that can be used when the pattern of missing data is arbitrary (monotone or non-monotone). The default number of iterations will be used (n=25) and, if needed, will be increased until the Markov chain converges. The seed will be "16075".

To allow comparison to Bagla (2016) results, a single imputation method, Last Observation Carried Forward, will also be performed, substituting the Treated Analysis Set's endpoint variable at the last available follow-up for the missing endpoint variable.

The analyses above are for the Primary Objective Report. For the Final Study Report, descriptive statistics, as well as confidence intervals, of the change in pain will be reported.

In the Primary Objective Report, the sensitivity analyses will include Treated Analysis Set subjects that have procedure dates before the last subject's procedure date in the Completers Analysis Set. In other words, subjects recently treated, but not expected to have been followed for the whole 3 months at the time of the snapshot, will not be in the sensitivity analyses.

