#### 13.3.6. Analysis Methods

A two-sided t-test with alpha=0.05 will be used to test the null hypothesis of no change in worst-pain score between baseline and 3 months.

If the distribution of the change scores does not meet the assumption of normality, the non-parametric Wilcoxon signed-rank test will be used to test for significant change with alpha=0.05, two-sided.

The primary objective hypothesis will be tested after the sample size requirements for it have been met. If additional subjects are enrolled later and also treated for metastatic lesions involving only the vertebral body, those additional subjects will be combined with the first group and summarized together.

The main analysis for the primary objective hypothesis testing will be on the Completers population.

In order to include all the treated subjects in the analysis, a sensitivity analysis will be performed on the Treated population. The endpoint data will first undergo multiple imputations (MI). Rather than filling in a single value for each missing value, MI replaces each missing value with a set of "plausible" values that represent the uncertainty about the correct value to impute. These multiple imputed datasets are then analyzed using standard statistical procedures and then combined into one analysis result with an appropriately increased variance. Included in the MI analysis will be the endpoint variable at 3 months and the endpoint variable at baseline, 3 days, 1 week, 1 month, and unscheduled visits (if collected), as well as baseline covariates. The method to be used is the Markov chain Monte Carlo (MCMC) method of SAS (version 9.4 or higher). This is an iterative method that can be used when the pattern of missing data is arbitrary (monotone or non-monotone). The default number of iterations will be used (n=5) and, if needed, will be increased until the Markov chain converges.

A single imputation method will also be performed, substituting the Treated population's endpoint variable at the last available follow-up (Bagla) for the missing endpoint variable.

Sensitivity analyses will be performed, separating the evaluation by whether or not the subjects received vertebral augmentation procedures and/or post RFA radiation therapy.

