### 7.9 Evaluation of Objectives

The primary objective hypothesis will be tested after the sample size requirements for it have been met. The sample size requirement is 35 subjects successfully treated and completing the pain assessment at 3 months. Prior to the date the 35th subject completes the 3-month visit, the visit cut-off date will be estimated for the database snapshot. If additional subjects are enrolled later and also treated for metastatic lesions involving only the vertebral body, those additional subjects will be combined with the first group and summarized together in the Final Study Report. However, no additional hypothesis testing will be performed in the Final Study Report.

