### 7.9.1 Primary Objective

To demonstrate an improvement from baseline to 3 months post radiofrequency ablation in worst pain score in the past 24 hours in subjects treated for metastatic lesions in only the thoracic and/or lumbar vertebral body(ies)

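### The SAP's success rule for the primary objective has no direction condition, so as written a significant worsening of pain would count as success (minor)

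*Combined protocol and SAP*

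**What the plan says.** SAP 7.9.1 states the objective directionally: "To demonstrate an improvement from baseline to 3 months post radiofrequency ablation in worst pain score in the past 24 hours", for subjects treated only in thoracic or lumbar vertebral bodies. The endpoint is the 3-month score minus the baseline score. A negative value is an improvement, and "a positive value represents an increase in the subject's pain score (a worsening, or increase in pain".

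The hypotheses are non-directional: mean change equal to zero against mean change not equal to zero. The analysis is a two-sided t-test at 0.05 on the completers, with the success rule "If the p-value is <0.05, the primary objective will be demonstrated, and statistical significance will be declared". If the Shapiro-Wilk test rejects normality, "the non-parametric Wilcoxon signed-rank test will be used to test for significant change with alpha=0.05, two-sided". Protocol 13.3.6 describes the same two tests; its t-test "will be used to test the null hypothesis of no change in worst-pain score between baseline and 3 months", again without reference to sign.

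On reporting, SAP 7.9.1 lists the t-test, the fallback, multiple imputation and last observation carried forward, and then says "The analyses above are for the Primary Objective Report". It continues: "For the Final Study Report, descriptive statistics, as well as confidence intervals, of the change in pain will be reported". On vertebral-only subjects who come later, SAP 7.9 says "those additional subjects will be combined with the first group and summarized together in the Final Study Report", and the hypothesis is not tested again.

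**The concern.** This is the study's only hypothesis test, and the sentence quoted from SAP 7.9.1 is the only place where the documents say what counts as success. It turns any two-sided p below 0.05 into a demonstrated objective. Because the objective is an improvement and the sign convention makes a positive change a worsening, the rule gives the wrong conclusion for one of the two ways in which the null hypothesis can be rejected. A pre-specified decision rule should give the right answer without the reader having to supply the missing condition.

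A lesser point concerns the estimate. The text available names confidence intervals for the primary endpoint only in connection with the Final Study Report. That report adds subjects who were not in the tested set, so its interval is not the interval that belongs to the test.

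**Working it through.** **Inputs.** From SAP 6: SD of change 3.5 (cited studies 2.4, 3.2 and 4.1), planned change 2 points, two-sided alpha 0.05, power 0.90, loss 32%. From SAP 7.9: 35 completers trigger the test. From the inclusion criteria: baseline worst pain of at least 4 on a 0 to 10 scale.

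**1. The plan's own figures.** Standard error = 3.5/√35 = 0.592. Noncentrality = 2/0.592 = 3.38. Critical value t(0.975, 34 df) = 2.032. Power from the noncentral t is 0.907 with n = 35 and 0.899 with n = 34, so 35 is correct. Treated subjects: 35/0.68 = 51.5, rounded up to 52. Both figures reproduce. The calculation enters the alternative as +2, although a reduction is negative under the endpoint definition. That has no effect on a two-sided calculation.

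**2. Probability that the rule as written declares success on a worsening.** This is P(T > 2.032), where T is noncentral t with 34 df and noncentrality (true mean change)/0.592.

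| True mean change | Noncentrality | Wrong-direction success, SD 3.5 |
|---|---|---|
| 0 | 0 | 2.5% (half of the 5.0% total) |
| +0.5 (worse) | 0.85 | 12.7% |
| +1 (worse) | 1.69 | 37.5% |
| −2 (planned) | −3.38 | 7.6e-8 |

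At the planned reduction the figure runs from 6.9e-12 (SD 2.4) to 9.3e-7 (SD 4.1).

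**3. With a sign condition added.** Success requires p<0.05 and a mean change below zero, which is the same as an upper 95% confidence limit below zero. Success under no true change falls from 5.0% to 2.5%. Power at the planned effect stays at 0.907, because the part removed is 7.6e-8. A one-sided 0.025 calculation also gives n = 35.

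**4. The whole path including the fallback.** Normal changes with SD 3.5 were simulated, rounded to whole points and put through the Shapiro-Wilk step at 0.05 (n = 35, 8,000 trials per case). The Wilcoxon test was used in fewer than one trial in ten. With no true change, success was about 5% under the literal rule and about 2.5% with the sign condition. With a 2-point reduction it was about 0.90 under both, and no trial succeeded in the wrong direction.

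**5. Effect of the bounded scale.** Steps 2 to 4 use unbounded changes. Entry at 4 or more limits a worsening to 10 − 4 = 6 points, and selecting subjects on high baseline pain favours a lower second score. For illustration, assume underlying pain with mean 6 and SD 2.5, a correlation of 0.3 to 0.7 between the two scores, and no treatment effect; none of these values is in the documents. Wrong-direction success was then below 0.5%. The 2.5% is therefore best read as an upper figure for the case of no effect.

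**6. The interval for the tested set.** Half-width = 2.032 × SD/√35 = 1.20 points at SD 3.5 (0.82 at SD 2.4, 1.41 at SD 4.1). If the goal of 100 vertebral-only subjects is met, all are treated and 32% are lost (assumptions), the Final Study Report has about 100 × 0.68 = 68 completers. If exactly 35 were tested, that is 35/68, or about 51% of them. SAP 7.9 sets the snapshot by an estimated cut-off date, so the tested number may differ from 35.

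**The case against.** The strongest reply is that no competent reader would apply the rule literally. The sentence refers to the primary objective, which the same section defines as an improvement, and the sign convention is given beside it. A two-sided 0.05 test is a normal choice for a directional objective. This stands, and it is why the point is minor. It does not remove the defect, because the sentence sets a sufficient condition for success and that condition is incomplete.

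A reader might go further and infer that the plan carries a real risk of presenting harm as benefit. The documents do not support that. The 37.5% arises only if mean pain truly rises by 1 point, at the planned effect the risk is negligible, and the no-effect figure is probably well below 2.5% on this scale.

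A reader might also infer that the SAP keeps the estimate and its interval out of the Primary Objective Report. The documents do not support that either. Nothing forbids them there. The limit to brief summaries in SAP 5 applies to subjects, non-primary efficacy and safety, not to the primary result. The protocol leaves presentation to report templates that are not among these documents. SAP 7.3 plans primary results by center, and multiple imputation gives a combined result for the treated set. SAP 5 also carries the original test result into the Final Study Report. None of these expressly promises an interval for the tested completers, but what remains is an unstated detail and not an error.

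**Conclusion.** The direction point holds as a minor error of wording. The rule in SAP 7.9.1 does not match its objective, and neither the fallback nor protocol 13.3.6 supplies the missing condition. Its size is at most 2.5% under no true change, about 37.5% if mean pain truly rises by 1 point, and about 8e-8 at the planned 2-point reduction. These figures rest on 35 completers, SD 3.5 and normally distributed changes. Sample size and power are not in question.

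The point about the estimate and interval holds only as missing detail in the text available. It merits an optional clarification.

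**What to change.** Replace the success sentence in SAP 7.9.1 with: *The primary objective is demonstrated if two-sided p<0.05 and the change is in the direction of improvement (t-test: mean change <0; Wilcoxon: negative rank sum exceeds positive rank sum).*

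Optionally add: *The Primary Objective Report will give the mean change in the Completers Analysis Set with its 95% confidence interval.*

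The cost is one sentence, or two with the option, and at most a line of output. No subjects are added: 35 completers, 52 treated and power 0.907 all stand. The chance of success under no true change falls from 5% to 2.5%. Whether protocol 13.3.6 needs matching words is for the sponsor to judge under its own amendment rule in protocol 13.1.

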#### **Table 9-1: Schedule of Events**

Events	Enrollment Baseline 	OsteoCool Procedure (Day 0) 	Prior to Discharge or within 12 hours of the procedure	3 days, 1 week, 1- ,3-,6-, and 12- Month Visits & unscheduled visits 	Phone eCRF (if needed)
Informed Consent Form 	Х				
Eligibility (Inclusion/Exclusion Criteria)	Х				
Pregnancy Test (Women of child-bearing potential)	X				
Demographics and Disease Characteristics	Х				
Karnofsky Performance Scale 	X 				
OsteoCool / procedure details		Х			
	Х	Х	х	Х	Х
Generator data uploads (if available)		Х			
PI assessment of local tumor control (optional)		х		х	
Concomitant cancer and/or tumor treatments, relevant to the target site(s)	х	Х		Х	Х
Concomitant pain medications 	Х	Х		Х	Х
Worst pain score only			Х		
BPI (Short Form) – includes worst pain score in the past 24 hours	Х			х	Х
EQ-5D-5L	х			Х	Х
EORTC-QLQ-C15-PAL 	X 			X 	
Deviations	Х	Х	X	X	Х
Event Review (AE/DD)	Х	Х	Х	X	Х

- 1) Informed consent must be obtained prior to performing any study-specific procedures.
- 2) Baseline Visit, Enrollment Visit and procedure can occur on the same day. Baseline visit shall be performed ≤ 21 days before the OsteoCool procedure
- 3) Oral narcotics within past 24 hours
- 4) Not applicable for subjects with benign bone tumors
- 5) Unscheduled visits will only be collected for visits conducted in the context of the study

Page 35 of 81

Table 9-2: Protocol Visit Windows\*

Visit	Visit ranges		
Enrollment/Baseline	NA		
Procedure (Day 0)	≤21 days after Baseline visit		
Discharge	Prior to hospital discharge or within 12 hours of the procedure		
Monthly Clinic Visits	3 Days: 3 days ± 2 Days after Day 0 1 week: 7 days± 2 Days after Day 0 1-Month Visit: 30 days ± 15 Days after Day 0 3-Month Visit: 90 days ±30 days after Day 0 6 Month Visit: 180 days ±59 days after Day 0 12 Month Visit: 365 days ± 90 days after Day 0		

\*Every attempt should be made to complete the required onsite clinic visit. However, if a subject is unable to complete an onsite follow-up visit due to physical circumstances, a Phone follow-up visit eCRF can be completed by the Investigator/RC to obtain the required data elements.

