### 7.1.3 Analysis Sets

#### **Analysis Sets**

There are 3 analysis sets:

**Enrolled**: all enrolled subjects. The demographics of this set, and specifically the subjects in this set but not in the Treated Analysis set, will only briefly be characterized. Otherwise, the efficacy and safety analyses will be on the following two analysis sets.

The analysis sets to be included in the efficacy analyses (primary objective, secondary objective, and additional measures) are described below.

**Treated Analysis Set**: all subjects who are successfully treated with the OsteoCool™ RF Ablation system.

**Completers Analysis Set**: the subset of Treated Analysis Set subjects who provided endpoint data at the 3-Month Visit. The Completers Analysis Set will be a subset of the Treated Analysis Set. The Completers Analysis Set will be the analysis population for the primary objective hypothesis testing.

The safety analyses will utilize the Treated Analysis Set.

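### SAP 7.9.1: the word *before* leaves at least one completer out of the sensitivity analyses, and later vertebral-cohort subjects have no planned imputation estimate in the Final Study Report (minor; primary test unaffected)

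*Combined protocol and SAP*

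**What the plan says.** SAP 7.9.1 introduces the missing-data check with a broad aim: "In order to include all the treated subjects in the analysis, a sensitivity analysis will be performed on the Treated Analysis Set". It describes MI by the MCMC method, then LOCF. SAP 7.1.3 fixes how the two sets relate: "The Completers Analysis Set will be a subset of the Treated Analysis Set".

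For the Primary Objective Report, the end of SAP 7.9.1 narrows the sensitivity set to "Treated Analysis Set subjects that have procedure dates before the last subject's procedure date in the Completers Analysis Set". A second sentence restates the rule: recently treated subjects "not expected to have been followed for the whole 3 months at the time of the snapshot, will not be in the sensitivity analyses".

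SAP 7.9.1 also divides the work between the two reports. After the test, MI and LOCF it says: "The analyses above are for the Primary Objective Report". It continues: "For the Final Study Report, descriptive statistics, as well as confidence intervals, of the change in pain will be reported". SAP sections 5 and 7.9 add that vertebral subjects treated later are pooled with the first group in the Final Study Report and summarised, without a further test.

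Three other places bear on this:

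- Protocol 13.3.6 plans MI and LOCF for the Treated population and ties them to no particular report. Protocol 13.1.4 defines that population as everyone successfully treated.
- SAP 7.9.2 plans imputation and a sensitivity analysis on the Treated Analysis Set for the secondary cohort, with no limit to one report.
- SAP 7.11 declares that nothing in the planned analysis has changed.

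**The concern.** There are two separate points in the same section.

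First, the operative sentence of the cut-off rule does not do what its own restatement says. Completers have a 3-month score by definition, so none of them should be removed by a rule aimed at short follow-up. A programmer coding the first sentence as written would still remove at least one. The MI and LOCF results would then omit an observed score that the primary analysis uses, and the two sets would not be nested as SAP 7.1.3 says.

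Second, the Final Study Report will describe the full vertebral cohort, but the visible text plans imputation estimates only for subjects inside the first report's cut-off. The completers analysis rests on an assumption, stated in SAP 7.4, that loss through death or deteriorating health is unrelated to pain level. MI and LOCF are the planned estimates that bring in treated subjects without a score. For later vertebral subjects no such estimate is planned, although the protocol sets no such limit and the secondary cohort has the check.

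**Working it through.** **Inputs.** From SAP 6: SD of change 3.5, difference 2 points, two-sided alpha 0.05, power 0.90, 32% without a 3-month score, and an enrolment goal of 100 vertebral-only subjects. From SAP 7.9: the test is triggered at 35 completers. Assumptions: all 100 are treated, the 32% holds throughout, and the first report's cut-off falls near the planned 52 treated.

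**1. The plan's own figures.** For a one-sample two-sided t-test using the noncentral t distribution, n = 35 gives power 0.907 and n = 34 gives 0.899, so 35 is right. Allowing for loss, 35 / (1 − 0.32) = 51.47, rounded up to 52. Both figures reproduce.

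**2. Who the cut-off removes.** Let m be the latest procedure date among the completers.

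- As written, a subject is kept if the procedure date is < m. The completer treated on date m fails, as does any other completer treated that day. At most 34 of 35 completers remain, and the set is about 51 rather than 52.
- If *last subject* means the last to finish the 3-month visit, with procedure date d, the rule keeps dates < d. That subject fails, together with any completer treated on or after d. The minimum loss is still one.
- With ≤ m, all 35 completers are kept.

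**3. Size of the first point.** Removing one of n values that lies a distance D from the mean moves the mean by D / (n − 1). With D = 3.5 and n = 52, this is 3.5 / 51 = 0.07 point. The standard error, using the same SD, is 3.5 / √51 = 0.49. The shift is therefore about one-seventh of a standard error (0.07 / 0.49 = 0.14). The primary test uses the Completers Analysis Set with no procedure-date cut, so it stays at n = 35.

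**4. What each text plans for imputation.**

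| Place | Cohort | Report |
|---|---|---|
| Protocol 13.3.6 | vertebral, Treated | no limit stated |
| SAP 7.9.1 | vertebral, Treated within the cut-off | Primary Objective Report |
| SAP 7.9.1, Final Study Report | vertebral, pooled | descriptive statistics and confidence intervals |
| SAP 7.9.2 | secondary, Treated | no limit stated |

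**5. Size of the second point.**

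- Missing scores in the final vertebral data: 100 × 0.32 = 32.
- Among the first 52 treated: 52 × 0.32 = 16.6, which the first report covers.
- Among the later 48: 48 × 0.32 = 15.4, which no imputation analysis covers.
- If only 90 are treated: 90 × 0.32 = 28.8 missing, of which 38 × 0.32 = 12.2 are not covered.

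**The case against.** On the first point, the best reply is that the SAP explains itself. The restatement identifies who is left out, and a completer is not among them; *up to* was almost certainly meant. The cut-off also deliberately narrows the general aim of including everyone treated. This stands as to intent, and it is why the point is a wording fix. It does not change what the first sentence instructs.

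On the second point, the imputation analyses can be seen as support for a single hypothesis test, performed once and not repeated. SAP 7.9.1 says what the Final Study Report will contain without forbidding more, and protocol 13.1.4 leaves room for further sensitivity analyses. The content of SAP 7.9.3 is not shown and could hold related analyses. All of this is fair. What remains is a mismatch between the protocol, which sets no one-report limit, and the SAP, which sets one while declaring no change.

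Four stronger readings are tempting but unsupported:

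- *The primary result is weakened.* It is not; the cut-off governs only the sensitivity analyses.
- *Missing data go unexamined in the Final Study Report.* SAP 7.4 has the frequency, timing and reasons for missing data reported and analysed, and SAP 7.1.1 summarises discontinuations. What they lack is an estimate that includes subjects without a score.
- *The final mean is biased by a known amount.* With 32% missing, a 1-point difference between missing and observed subjects would move the all-treated mean by 0.32 point, and a 2-point difference by 0.64. Those differences are hypothetical, and the uncovered group accounts for only about 0.15 per point (15.4 / 100). MI under missing-at-random, or LOCF, need not recover such a shift.
- *The cut-off mislabels many pending scores as missing.* The visit window is wide ("3-Month Visit: 90 days ±30 days after Day 0"), so a subject treated before the last completer may still be awaiting the visit at the snapshot. How many depends on accrual and visit timing that the documents do not give, and there are none if every visit falls on day 90. The restated rule already addresses subjects with short follow-up, so no change is proposed there.

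**Conclusion.** Both points hold and both are minor. The first is certain on the literal wording: at least one completer is left out of MI and LOCF in the Primary Objective Report, contrary to the stated aim and to the rule's own restatement. The practical effect is small.

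The second rests on the visible text of SAP 7.9.1 set against protocol 13.3.6, SAP 7.9.2 and SAP 7.11. About 15 vertebral subjects without a score would never enter an imputation analysis if the goal of 100 is reached, all are treated and loss is 32%; with 90 treated the figure is about 12. The goal is an enrolment goal, so the treated number may be lower. Whether the omission would hide any bias, and in which direction, cannot be determined from the documents.

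**What to change.** 1. In SAP 7.9.1, replace the cut-off phrase with: *on or before the procedure date of the last-treated subject in the Completers Analysis Set*. This keeps every completer and settles which subject is the last. Leave the snapshot, and the handling of subjects awaiting their 3-month visit, as they are. The cost is one phrase.
2. In the Final Study Report, repeat the existing MI and LOCF analyses on all treated vertebral-cohort subjects. Present them as estimates with confidence intervals and no hypothesis re-test. This brings the SAP back in line with protocol 13.3.6 and spends no alpha. The cost is one rerun of existing programs and one table. If SAP 7.9.3 already provides this, a cross-reference is enough.
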